4.4 Interim Analyses and Data Monitoring

One formal interim analysis is planned when 2/3 of the required total number of primary efficacy endpoint events have been observed.

If the interim analysis shows clear and consistent benefit in the finerenone treatment group, the DMC may recommend early study termination. The Haybittle-Peto rule will be used to guide the decision regarding early stopping of the study for success: a reduction of 3 standard deviations in the analysis of the primary and the key secondary efficacy endpoint at the interim analysis (two-sided p-value <0.00270).

For a detailed description of the testing procedure, including an adjustment of the significance level for the interim analysis, please see section 4.7.

In case of an early stop of the study for success, the final analysis reported in the CSR will consider all events up to the subjects' respective EoS visits as would have been the case if the study had not stopped early. A sensitivity analysis will take all events up to the interim analysis datacut date into consideration and will be based on the same final clean database as done for the final analysis reported in the CSR (instead of the interim analysis database). For this sensitivity analysis, censoring dates after the datacut date will be reset to the datacut date.

For a lack of efficacy, a non-binding futility approach will be utilized at the time of the planned interim analysis. If the conditional probability of rejecting the null hypothesis for the primary comparison, given the assumed and current event rates, falls to an unacceptably low level (as specified in the DMC Charter), the DMC may consider recommending early termination of the study.

A detailed plan for the routine DMC safety analyses and the interim analysis is covered in the DMC charter, the analysis planned to be provided to the DMC is described in a separate DMC SAP with Tables, Listings and Figures (TLFs) attached to the DMC charter. The DMC will review the data in an unblinded manner, both for the routine safety tables and the interim analysis. There are no predefined stopping conditions for the ongoing safety monitoring of this trial. The statistical analysis for the DMC meetings will be performed by an independent statistical analysis center.

4.5 Data Rules

General data rules are described in this section, further data rules for specific parameters or analyses are specified in the respective subsections of section 6.

4.5.1 Baseline values

Baseline values will be defined as the last non-missing measurement before or on the day of randomization. If the last observation available prior to randomization is the measurement from the Screening Visit, this would be used as the baseline value. This also includes assessments from a local laboratory, in case that prior to randomization, no assessment from the central laboratory is available. Otherwise baseline will be missing. The measurement from the Run-in Visit will not be used as a baseline value unless otherwise specified.

If more than one measurement was planned for a scheduled visit, for example blood pressure measurements and heart rate, the mean value of these measurements per time point prior to randomization will be used as the baseline value.

4.5.2 Change from baseline

Change from baseline will in general be displayed as absolute change from baseline defined as the difference to baseline, i.e.:

$$\text{Absolute change} = \text{Post baseline value} - \text{baseline value.}$$

Some parameters will be additionally analyzed as relative change defined as

$$\text{Relative change} = 100 * [(\text{post baseline value} - \text{baseline value}) / \text{baseline value}].$$

For specific analyses, the relative decrease of a variable will be analyzed instead of the relative change. The relative decrease is equivalent to the negative of the relative change and defined as

$$\text{Relative decrease} = 100 * [(\text{baseline value} - \text{post baseline value}) / \text{baseline value}].$$

4.5.3 Other data handling

Only the data provided by the central laboratory will be used for analysis, values from local laboratories will not be used in the statistical analysis and will be listed only unless there are no values from the central laboratory available for baseline.

In case of retests for Run-in and Screening visits, the closest measurement prior to randomization will be used for analysis instead of the scheduled measurements. At all visits starting at Visit 1 and if not stated otherwise, only the values at scheduled measurements will

be used for analysis. In the unexpected case that more values than planned are available for a scheduled visit, only the first valid value will be used.

For the derived visit “Any time post-baseline” (applicable for efficacy) this will include any measurement after date of randomization, including unscheduled assessments. For the derived visit “Any treatment-emergent” (applicable for safety), only assessments on or after study medication start date until 3 days after the date of any temporary or permanent interruption of study drug, including unscheduled assessments, will be considered.

For those laboratory values which are <LLOQ (Lower limit of quantification), half the value of the LLOQ will be used for analysis. Differences between 2 values <LLOQ will be assigned values of 0. Ratios between 2 values <LLOQ will be assigned a value of 1. For values which are >ULOQ (Upper limit of quantification), the ULOQ will be used for analysis. This rule does not apply to the finerenone plasma concentration data.

In case of log-normally distributed data, descriptive statistics other than minimum, maximum and median will only be calculated if at least 2/3 of the individual data were measured and were above the lower limit of quantification. In tables showing descriptive statistics, where values below LLOQ are included, these descriptive statistics will be marked.

Urinalysis is assessed 3 times per visit. UACR will be determined 3 times at each visit from first morning void urine samples collected on 3 consecutive days. For the analyses of UACR, the 3 measurements at one visit will be combined provided that at least 2 measurements are available. First, the coefficient of variation (CV) will be calculated for the 3 values as follows considering the log-normal distribution for UACR [7]:

$$CV = \sqrt{\exp(SD_{\ln}^2) - 1},$$

where SD_{\ln} is the standard deviation of the 3 log-transformed UACR values. If the coefficient of variation exceeds 25%, the median from the measurements will be used for the analyses. The median in case of an even number of values will be defined as the geometric mean from the 2 middle values. If the coefficient of variation is 25% at the most, the geometric mean will be used. If 2 or all 3 scheduled assessments are missing or invalid and unscheduled assessments have been performed, then the set of unscheduled measurements closest to the planned visit will be used to determine the UACR at the respective visit if performed within 30 days before or after the planned time point for all visits from Visit 3 (Month 4) onwards (with the following exception: only samples with 2/3 of values no later than 30 days (for “last on-treatment” analysis) or 3 days (for “last treatment-emergent” analysis) after last study drug intake will be considered). For Visit 1, 2 out of 3 samples have to be on or before the day of randomization and have to lead to non-missing values in order for the set of samples to be valid for baseline calculation; otherwise (also including the case when there is one valid sample at Visit 1), the set of screening samples will be considered for baseline.

In the case of ESRD, the UACR and eGFR values after the onset date of ESRD will be excluded from all efficacy analyses, but included in the safety analyses.

For the stratification group type of albuminuria at screening (high or very high), the classification supplied from the central lab via IxRS will be used. The rule that has been applied by the central lab for this classification is, if there are 3 values, the median value

should be taken; if 2 values, then the arithmetic mean value, regardless of degree of variation between the values. The lab reports from the run-in and screening visits will include the type of albuminuria, to assist the investigators in reducing stratification and randomization errors.

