Study drug administration			X		X						
KDQOL-36, EQ-5D-5L			X				X		X	X	
Physical examination	X	X					X		X	X	
Weight, height, waist and hip circumference ^a	X	X	X	X	X	X	X	X	X	X	
Vital signs ^b	X	X	X	X	X	X	X	X	X	X	
12-lead ECG (local)	X	X	X				X		X	X	
PK blood sample					X ⁿ		X ^o				
Full central laboratory	X	X	X		X	X	X		X	X	
Limited chemistry (central)				X				X			
Urinalysis (central) ^c	X	X	X		X		X			X	
Safety laboratory (local) ^d			X	X	X	X	X	X			
Endpoint assessment ^e				X	X	X	X	X	X	X	
AE assessment ^f	X	X	X	X	X	X	X	X	X	X	X
Pregnancy test ^g		X					X				

Table 9–1 Study 17530: schedule of activities and evaluations - amended**NOTE:**

One month corresponds to 30 days

A time frame of ± 7 days is allowed for Visit 2 (Month 1), and for the Up-titration Visit(s).

A time frame of ± 12 days is allowed for all regular visits from Visit 3 (Month 4) onwards.

Abbreviations:

ECG = electrocardiogram; EOS = end of study; EQ-5D-5L = EuroQoL Group 5 dimension, 5 level questionnaire; KDQOL = Kidney Disease Quality of Life;

PD = premature discontinuation; PT = post-treatment; (S)AE = (serious) adverse event; SD = study drug

- ^a Height, waist and hip circumference to be assessed at Run-in Visit only.
- ^b After resting for at least 5 minutes, 3 measurements to be taken with at least 1-minute interval in a sitting position (all 3 readings within a maximum of 20 minutes).
- ^c At Visit 1, first morning void urine samples to be preferably collected on three consecutive days at the subject's home within 7 days before scheduled visit and before any intake of study drug. At the other visits the 3 consecutive samples can be collected ± 7 days from the visit date.
- ^d Blood samples (for potassium and creatinine) for measurement in the local laboratory may be obtained up to 72 hours before a scheduled visit. Samples to be taken only if the subject is still taking study drug.
- ^e Categorical renal endpoints, $\geq 40\%$ or $\geq 57\%$ decrease in eGFR compared to baseline and an eGFR decrease to less than 15 mL/min/1.73 m², have to be confirmed by at least one additional standardized serum creatinine measurement. This confirmation should be done at least 4 weeks after the initial measurement as an unscheduled assessment.
- ^f AEs related to study procedures occurring after signing the informed consent as well as all other AEs starting after randomization will be documented on the respective eCRF pages.

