9.2.10 End of study (EOS) visit - amended

This section was changed in Amendment 3, see Section 15.1.2.23.

The following procedures and assessments will be performed at the EOS Visit:

- The subject completes KDQOL-36 and EQ-5D-5L questionnaires (see Section 9.7.7)
- Record use of concomitant medication (see Section 8.1)
- Collect unused study drug and perform accountability to assess compliance (see Section 7.6)
- Perform physical examination (see Section 9.7.3)
- Record body weight (see Section 9.7.4)
- Record vital signs (see Section 9.7.5)
- Perform 12-lead ECG (see Section 9.7.6)

- Take samples (hematology, HbA1c, chemistry, urinalysis) for central laboratory evaluations (see Section 9.7.2.1)
- Optional: if the subject had signed informed consent for the sub-study, obtain respective samples for biomarkers (see Section 9.7.8.1.2) and/or for iohexol clearance (see Section 9.7.8.1.3), perform echocardiography (see Section 9.7.8.1.1)
- Assess if the subject has any endpoint event(s) (see Table 13–1 and Section 9.6.1.3.1)
 - Any eGFR declines that meet endpoint criteria that are identified at the EOS Visit, or that cannot be confirmed by the time of the EOS Visit, should be confirmed 4 weeks after the initial decline
- In exceptional circumstances only, if the subject is unable to attend this visit during the given timeframe, the subject (or primary physician / next of kin) should be contacted to obtain survival status.
- Record adverse events (see Section 9.6.1), accounting for the rules of assessment and documentation (see Section 9.6.1.3).

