9.2.11 Post-Treatment (PT) Visit - *amended*

This section was changed in Amendment 3, see Section 15.1.2.24.

For all subjects (except those who participate in the iohexol clearance study) who are still on treatment with study drug at the end of study visit, this will be performed by telephone contact within 4 weeks + 5 days after last study drug intake. The following will be performed at the PT Visit:

- Record use of concomitant medication (see Section 8.1)
- Record adverse events (see Section 9.6.1), accounting for the rules of assessment and documentation (see Section 9.6.1.3).

For subjects who signed informed consent for the iohexol clearance sub-study, the PT Visit will be performed as an on-site visit with the following procedures and assessments:

- Record use of concomitant medication (see Section 8.1)
- Obtain samples for iohexol clearance (see Section 9.7.8.1.3)
- Record adverse events (see Section 9.6.1), accounting for the rules of assessment and documentation (see Section 9.6.1.3).

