10.1 General considerations

Statistical analysis will be performed using SAS; the version used will be specified in the statistical analysis plan (SAP).

A log-normal distribution is assumed for serum creatinine and UACR. For all other metric variables, a normal distribution is assumed. The distributional assumptions will be investigated and if necessary, nonparametric methods or transformation of the data will be considered.

All variables will be analyzed by descriptive statistical methods. The number of data available, mean, standard deviation (SDv), minimum, median, and maximum will be calculated for metric data. The geometric mean and SDv will be provided instead of the arithmetic mean and SDv for the variables where lognormal distributions are assumed. Frequency tables will be generated for categorical data.

Baseline values will be defined as the last non-missing measurement before randomization (Visit 1). If the last observation available prior to randomization is the measurement from the Screening Visit, this would be used as the baseline value. This also includes assessments from a local laboratory, in case that prior to randomization, no assessment from the central laboratory is available. Otherwise baseline will be missing. The measurement from the Run-in Visit will not be used as a baseline value. If more than one measurement was planned for a scheduled time point, for example blood pressure measurements and heart rate, the mean value of the last set of measurements per time point prior to randomization will be used as the baseline value.

Only the data provided by the central laboratory will be used for analysis, values from local laboratories will not be used in the statistical analysis and listed only.

In the event of repeated measurements for Pre-treatment Visits and the Visit 1 (Day 1; baseline), the closest measurement prior to randomization will be used for analysis instead of the scheduled measurements. At all visits post-randomization and unless stated otherwise, only the values at scheduled measurements will be used for analysis.

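### Does the SAP's scheduled-values rule shut out the unscheduled re-test that confirms an eGFR endpoint, above all for a decline first seen at the End-of-Study visit?

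*SAP*

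**What the plan says.** The general data rule in SAP 4.5.3 is that "At all visits starting at Visit 1 and if not stated otherwise, only the values at scheduled measurements" are used. For surplus values it adds: "In the unexpected case that more values than planned are available for a scheduled visit, only the first valid value will be used". Re-tests are admitted by name only before randomization: "In case of retests for Run-in and Screening visits, the closest measurement prior to randomization will be used for analysis". Protocol 10.1 has the matching rule: "At all visits post-randomization and unless stated otherwise, only the values at scheduled measurements will be used for analysis". SAP 4.5.3 carries its own exceptions. Where scheduled UACR samples fail, "then the set of unscheduled measurements closest to the planned visit will be used to determine the UACR at the respective visit", and the derived visit for any time after baseline takes in unscheduled values.

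On the confirming eGFR value, Protocol Table 9-1, footnote e, says: "This confirmation should be done at least 4 weeks after the initial measurement as an unscheduled assessment". Protocol 9.2.10 extends this to the last visit: "Any eGFR declines that meet endpoint criteria that are identified at the EOS Visit" are to be confirmed 4 weeks later. No scheduled eGFR exists by then. For most subjects still on drug the Post-Treatment Visit is a phone call ("this will be performed by telephone contact within 4 weeks + 5 days after last study drug intake"). In the iohexol sub-study it is on site, but without an eGFR sample.

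SAP 6.2.2.1 counts renal events up to the last visit with complete information on all components. It censors event-free subjects no later than EOS, and allows later events only for kidney failure and renal death. It mentions neither re-tests nor the date of a sustained decline.

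Two further rules matter. SAP 4.1 limits efficacy analyses to adjudicated outcome events, apart from the investigator-reported tables. Protocol 13.1.2 and Table 13-1 send eGFR declines to the Clinical Event Committee (CEC) as events that already include the confirming measurement.

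**The concern.** Read side by side, SAP 4.5.3 admits scheduled values only, and the confirming value is unscheduled by definition. The authors wrote exceptions for UACR and for pre-randomization re-tests, so silence on the eGFR re-test could look deliberate. For a decline first seen at EOS the re-test is the only possible confirmation, and it comes after the point at which SAP 6.2.2.1 stops following event-free subjects.

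The composite with the 40% decline is the key secondary endpoint. At the final analysis it stands directly after the primary endpoint and ahead of four further secondary tests (SAP 4.7). The event date also decides whether such a decline enters the per-protocol and on-treatment analyses, which stop 30 days after last intake. If the plan truly left open whether these events count, the choice could be made after unblinding.

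**Working it through.** No figure in the plan depends on this point, so there is none to reproduce. The check sets the passages against each other and sizes what the literal reading would cost.

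**1. Timing.** Take notification of study termination as day 0. EOS falls on days 0 to 28, and a re-test comes at least 28 days after the first low value.

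| EOS day | Earliest re-test | Days after EOS |
|---|---|---|
| 0 | 28 | 28 |
| 14 | 42 | 28 |
| 28 | 56 | 28 |

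So confirmation of a decline first seen at EOS always follows EOS. If the last dose is taken at EOS, the first low value (0 days after last dose) lies inside the 30-day window. A re-test lies inside it only on days 28 to 30.

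**2. Which rule governs.** SAP 4.5.3 handles visit values and yields where something else is stated. The renal composites are not built from visit values. They come from adjudicated events (SAP 4.1), and the event as adjudicated contains its confirmation (Table 13-1). Taken literally, SAP 4.5.3 would void every unscheduled confirmation in the trial, not only those after EOS. Confirmation would then wait for the next regular visit, 120 days on (96 to 144 days if both visits use their 12-day windows), against footnote e. SAP 4.8 classes a missed eGFR re-test as missing data, which makes sense only if re-tests are endpoint data. The surplus-value rule concerns several values at one visit, not a sample taken weeks later.

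**3. The EOS limit.** The words in SAP 6.2.2.1 that stop at EOS set the censoring date of subjects without an event. A decline first measured at EOS lies on that visit, so it is inside the limit if dated at first measurement. The allowance for kidney failure and renal death covers events after the last recorded eGFR. An EOS decline is not one of those, so its absence from the allowance excludes nothing. The cut-off at notification plus 4 weeks in SAP Appendix A is the horizon for imputing events in withdrawn or lost subjects, not a limit on confirmation data.

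**4. The date.** SAP 4.3 speaks of the adjudicated event date, and SAP 6.2.3 of time to onset of the eGFR decrease. Both suggest the first low value, but neither defines it. The SAP lists the CEC Charter among its source documents, and Protocol 9.4 places the remaining endpoint definitions in the Endpoint Manual. Neither was available here.

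**5. Size if the literal reading were applied.** Inputs are Protocol 10.4 (recruitment 33 or 41 months, total 44 or 48 months, uniform entry) and visits every 4 months. Follow-up T is uniform on 11 to 44 or on 7 to 48 months, and L is the last regular visit before EOS.

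- *Constant hazard*: share first seen at EOS = mean(T − L) / mean(T). Mean T = 44 − 16.5 = 27.5, and 48 − 20.5 = 27.5. Mean gap = (1 × 3.5 + 32 × 2)/33 = 2.045, and (1 × 3.5 + 40 × 2)/41 = 2.037. Share = 7.4% in both.
- *Hazard rising linearly*: share = 1 − mean(L²)/mean(T²).
  - 33/44 plan: mean T² = (44³ − 11³)/(3 × 33) = 847; mean L² = (64 + 64 × 380)/33 = 738.9; share 12.8%.
  - 41/48 plan: mean T² = (48³ − 7³)/(3 × 41) = 896.3; mean L² = (16 + 64 × 505)/41 = 788.7; share 12.0%.

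Here 380 and 505 are the sums of m² for m = 3 to 10 and m = 2 to 11, where regular visits fall at month 4m. Simulation gave the same shares. With the SAP's randomization dates (October 2015 to January 2019, 39 months) and an assumed total of 60 to 64 months, it gave 4.6% to 9.1%. Adding declines first seen less than 28 days before EOS raises the two ranges to 10.7–17.9% and 6.5–12.8%.

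**The case for a change.** The best case for a change is that adjudication decides whether a decline is confirmed, while the SAP alone decides the counting window and the censoring date. That window ends at EOS, and whether an adjudicated EOS decline falls inside it depends on a date the SAP never defines. SAP 6.2.4 says that final missed eGFR measurements are handled by the censoring rules of SAP 6.2.2.1, yet that section does not mention re-tests. It is also unstated whether an EOS visit with a low, un-retested value has complete information. On an endpoint this high in the hierarchy, a sentence written before unblinding costs almost nothing.

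Part of this stands. The SAP does not restate the event date, and the documents that may define it were not seen. A cross-reference would be tidy. But it would record what adjudication and the onset wording already lead an analyst to do, and would alter no result.

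The un-retested subject is a real but small gap. At stake is the censoring date of a subject without a confirmed event, normally by about one visit interval. The obvious alternative, moving that subject back to an earlier visit, ties censoring to a low outcome value and is no clear improvement.

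A re-test after EOS is off drug for those who stop at EOS, so confirmation could differ by arm if an acute effect reverses. Wording on dates would not touch that, since the same re-tests would be accepted. The documents give no size for it; Protocol 3.3 reports similar rates of declines of at least 30% between groups in the 90-day Phase II study.

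**Conclusion.** No change follows. SAP 4.5.3 does not exclude the confirming re-test, because adjudicated events, not visit values, feed the renal composites. Protocol 9.2.10 expressly provides for confirmation after EOS. What remains is an unstated detail, the date of a sustained decline, which an analyst would fill sensibly with the first low value. So dated, a decline first seen at EOS counts in the full-analysis-set test and in the 30-day analyses for subjects who take their last dose at EOS.

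The 7.4% to 12.8% share sizes only a reading that contradicts the protocol's own schedule. It rests on assumed hazard shapes and applies to the eGFR components, not to the whole composite. It implies no bias and no shift in the hazard ratio.

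The conclusion assumes that the CEC Charter and Endpoint Manual do not date the event at the confirming measurement. If they did, the passages would need to be reconciled. The primary cardiovascular endpoint, its event target and its power do not depend on any of this.
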